Hypothesis: The WBF and FPS-R will demonstrate convergent validity when used to measure acute pain in children presenting to the emergency department

Rationale: Both the WBF and FPS-R have been studied for their use in obtaining self-reports of pain in children, and overall have been determined to be two of the preferred methods of pain assessment in pediatric patients. Although each has been compared to other methods of pain measurement, the two have not been compared to each other. If the two studies were proven to have convergent validity, it would strengthen the evidence that these methods should be the preferred tools for assessing pain in children.

Methods Summary: Prospective, observational study to determine the convergent validity of the WBF and FPS-R for children presenting to the ED with acute pain. The initial and repeat WBF and FPS-R self-report scores will be compared in patients presenting to the ED with acute pain.

Phase 2 – Secondary Aim #2

To determine if there is inter-rater reliability between patients presenting to the pediatric ED with acute pain and their caregivers when using the WBF and FPS-R at two separate time points during their ED evaluation

Hypothesis: There will be low inter-rater reliability between patients and their caregivers using the WBF and FPS-R.

Rationale: Caregiver perception of a pediatric patient's pain is often used as a substitute for the patient's self report of pain; however, studies are limited to show that caregivers are able to predict children's pain level accurately when in the acute care setting.

Methods Summary: Prospective, observational study to determine the inter-rater reliability between patients and their caregivers when using the WBF and FPS-R. The initial and repeat WBF and FPS-R self-report scores will be compared to caregivers' initial and repeat WBF and FPS-R ratings in patients presenting to the pediatric ED with acute pain.

Identification of Subjects

Participants will come from a convenience sample of children presenting to the ED. Triage nurses and ED providers will be aware of the study and notify the PI or designee by phone if patients may qualify for the study. The PI and designees will also have access to the ED trackboard and can screen for possible participants.

Inclusion Criteria

Patients \geq 3 years and \leq 7 years six months old Chief complaint of pain or painful condition (Phase 1 only) Pain score \geq 4/10 (Phase 2 only) Caregiver speaks English or Spanish

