Exclusion criteria

Altered mental status History of traumatic brain injury (TBI) History of developmental delay History of Autism History of chronic pain, defined as persistent or recurrent pain in children with chronic health conditions⁸ Non-verbal patients

Outcome Measures:

Phase 1 - Primary Aim

Rate of intended script use in pain scale delivery Review of themes during nursing pain assessment Consistency in delivery of WBF by nursing

Phase 2 - Primary

Neurocognitive development score BRIGANCE ® score Initial WBF score Repeat WBF score Initial FPS-R score Repeat FPS-R score Anchor report of pain (a lot better, a little better, the same, a little worse, a lot worse)

Phase 2 - Secondary

Initial WBF score (patient and caregiver) Repeat WBF score (patient and caregiver) Initial FPS-R score (patient and caregiver) Repeat FPS-R score (patient and caregiver)

Study Definitions:

"Caregiver" will refer to an adult who is able to provide consent for treatment and provides regular care for the child.

"Chronic pain" includes persistent (ongoing) and recurrent (episodic) pain in children with chronic health conditions.

Convergent validity evaluates the degree to which two different scales that are supposed to measure the same thing produce similar results.

"Repeat pain score" will be completed approximately 20 minutes after the initial pain score, or if administered, approximately 20 minutes after analgesic intervention.

Responsivity is the degree to which a test behaves in a manner that is consistent with what the test is purported to measure. It determines whether the measure is able to identify changes in pain over time that are clinically important to patients.

Phase 1 Study Protocol:

- 1. Once the subject is identified, the caregiver will provide verbal consent for participation in the study.
- 2. After verbal consent is obtained, the primary investigator will observe and audio record nursing's assessment of the patient's pain and complete the observation checklist (Appendix 1).

Phase 2 Study Protocol:

- 1. Once the subject is identified, the caregiver will provide written consent for participation in the study (if a self-report pain score was not collected in the triage process, patients with pain or a potentially painful condition will have their pain assessed using an age appropriate self-report pain scale by the PI or designee).

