Responsivity will be measured by correlating the change in the WBF and FPS-R scores before and after analgesic intervention with the anchor change in pain score (a lot better, a little better, the same, a little worse, a lot worse). Pearson correlations will be estimated between each change score and the anchor score. In addition, we will use ANOVA to test the difference in mean pain change among the children reporting "a lot better", "a little better", and "the same". For the scales to be considered responsive, we would need to see significant reductions for the children reporting "a lot better", minimal to no reduction for those reporting "the same", and increase in pain for those reporting "worse". We will need a relatively large number of children in each category (a lot better, a little better, the same) to be able to test for differences (at least 30 per group). We will use Fisher's z-transformation to test if level of neurocognitive development impacts responsivity. Levels of neurocognitive development will be defined as at or above expected or lower than expected. The Fisher's z-transformation formally tests if the correlations between two measures (change in pain and anchor rating) differ between two groups. Here we assume we will have significant variability in change scores and in the anchor ratings to conduct these correlations and the formal test. We would need at least 56 children in each neurogcognitive development group (expected or above versus below). If the variability is limited in that most children report improvement and few report same or worsening, we will test for responsivity differences using a two-way ANOVA where the two factors are self reported anchor response ("better", "same" or "worse) and neurocognitive level (expected or above expected vs below expected). The outcomes are the change in the WBF and the change in the FPS-R. The test of interest will be the two way interaction between the anchor and the neurocognitive development level. The BRIGANCE also provides the developmental age for each child which can be compared to their actual age. We will test if this difference is significant using a paired t-test. We will also explore the age where responsivity worsens by conducting similar analyses but stratified by actual age (each year) and developmental age. Given the proposed analysis, we will need at least 50 children for each cognitive age (3, 4, 5, 6, and 7 years) assuming at least 10 fall into the "a lot better", "a little better", "the same" categories for the anchor pain question.

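### Phase 2 responsivity is tested on raw change with no term for the initial score, which costs precision and could let a large gap in starting pain pass for a difference in responsivity

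*Combined protocol and SAP*

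**What the plan says.** All of this is in the Phase 2 part of Statistical Analysis.

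- **Basic measure.** "Pearson correlations will be estimated between each change score and the anchor score". A one-way ANOVA then compares mean change across three anchor categories (a lot better, a little better, the same).
- **First-choice test for Primary Aim #1.** The change-anchor correlations are compared between two developmental groups by Fisher's z. "Levels of neurocognitive development will be defined as at or above expected or lower than expected".
- **Fallback.** "If the variability is limited in that most children report improvement and few report same or worsening", the plan moves to a "two-way ANOVA where the two factors are self reported anchor response", in three levels, and neurocognitive level. "The test of interest will be the two way interaction between the anchor and the neurocognitive development level". On the dependent variable: "The outcomes are the change in the WBF and the change in the FPS-R".
- **Age analyses.** Similar analyses are repeated by actual and developmental age.

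The initial score is neither a covariate nor a stratifier in any of these. It is available: Outcome Measures lists "Initial WBF score Repeat WBF score Initial FPS-R score Repeat FPS-R score", and Part One of the Patient Survey (Appendix 3) records both scales. Apart from forming the change, initial scores serve only convergent validity and the parent-child ICCs.

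**The concern.** The faces run 0, 2, 4, 6, 8, 10, and Phase 2 entry requires a pain score of at least 4. A child who starts at 4 can fall two faces, and one who starts at 10 can fall five. Two children who both say they are a lot better may therefore show very different changes only because of where they began. That spread enters the residual variance of every analysis of change.

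The neurocognitive groups are observed in a convenience sample, so nothing balances their starting pain. If one group starts higher and change depends on starting pain differently across anchor categories, part of that gap appears as a difference in responsivity. That would bear directly on Primary Aim #1.

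**Working it through.** **The plan's own figures.** The total agrees with its parts: 5 cognitive ages x 50 = 250. The 56 per group is given without alpha, power or correlations, so it cannot be uniquely reproduced. Assuming two-sided 0.05, 80% power and correlations of 0 and 0.5, n = 2 x ((1.960 + 0.842)/0.5493)² + 3 = 55.02, rounded up to 56. Other pairs give the same number. Neither figure depends on baseline adjustment.

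**Precision.** With equal variances and initial-repeat correlation rho, the variance of change is 2σ²(1 − rho) and the residual variance after adjustment is σ²(1 − rho²). The ratio is (1 + rho)/2. The documents give no rho, so a range is shown:

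| rho (assumed) | Ratio | Reduction |
|---|---|---|
| 0.2 | 0.60 | 40% |
| 0.5 | 0.75 | 25% |
| 0.8 | 0.90 | 10% |

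Simulation of the anchor ANOVA on the bounded scale agrees. Residual variance fell from about 4.1 to 2.7 with relief proportional to starting pain (1.4/4.1 = 34%), and from 3.4 to 3.0 with additive relief (0.4/3.4 = 12%).

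**How a false interaction arises.** Assume an anchor mix of 35/30/25/10% (a lot better, a little better, same, worse) and proportional falls of 70%, 35% and 0% in the first three categories. In the pooled 'better' level the mean fall is (0.35 x 0.70 + 0.30 x 0.35)/0.65 = 0.538 of starting pain. Ignoring rounding and scale limits:

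- Starts of 7.5 and 5.5: falls of 4.04 and 2.96 among 'better', none among 'same'. The spurious better-versus-same contrast is 1.08 points.
- A one-point gap: 0.54 points.
- Additive relief (the same number of points from any start): 0.

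With 194 and 56 children, the 'better' and 'same' cells hold 126.1, 48.5, 36.4 and 14.0. At a simulated residual variance of 4.07, the standard error is √(4.07 x (1/126.1 + 1/48.5 + 1/36.4 + 1/14.0)) = 0.72. The contrast is thus about 1.5 standard errors at a two-point gap and 0.75 at one point.

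**Simulated rejection rates at a nominal 5%, with no true difference in responsivity** (250 children, split 194/56 or 125/125; starts, SDs, measurement error and anchor mix all assumed):

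| Setting | Planned interaction, no initial score | Fisher z |
|---|---|---|
| Additive relief, gap 0 to 2 points | 4% to 6% | 2% to 3% |
| Proportional, equal starts | 2% to 5% | about 3% |
| Proportional, one-point gap | 2% to 5% in most three-level runs; 8% to 10% in others | 7% to 8% |
| Proportional, two-point gap | at most 12% in the lowest three-level set; up to 39% in the highest set | 11% to 32% |

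**What adjustment does to the interaction test at a two-point gap.** The initial score as a main effect alone makes matters worse: 31% or more across sets. Adding initial score x anchor brought the rate to about 5% in one set and 10% in another that used robust standard errors (against 41% unadjusted there), but left up to 20% in the least favourable set. Some excess remains because the initial score is itself measured with error.

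**The case against.** The strongest reply has four parts.

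1. **Raw change against an anchor is a recognised responsiveness measure**, and the plan judges responsivity by mean change within anchor category. This stands. It is a reason to keep the planned analysis and put the adjusted one beside it.
2. **The false signal needs two conditions that the documents do not state**: a material gap in starting pain between developmental groups, and change that depends on starting pain differently by anchor category. This also stands. A reader might infer that the plan's test of Primary Aim #1 has an inflated error rate as written. The documents do not support that. One simulation gave 16% at a one-point gap, but other runs with four anchor levels gave 5% to 7%, and the plan's fallback has three levels.
3. **The interaction test is only the fallback.** A reader might take it as the test that answers Primary Aim #1, but the plan gives that role to Fisher's z. This corrects the emphasis without removing the point, because the Fisher z comparison also ignores starting pain and was the more sensitive of the two at a one-point gap in most runs.
4. **Adjustment has a price where data are thin.** The fallback applies when few children report no change or worsening. At 10%, a group of 56 has about 6 'worse' children. In one set of runs with four anchor levels and few non-improvers, the model with initial score x anchor rejected 8.6% against 5.2% for the plan. This stands, and is a further reason for a companion model and not a replacement.

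**Conclusion.** The omission is real and covers every Phase 2 responsivity analysis. The firm part is precision: a reduction of roughly 10% to 40% in the residual variance of the anchor ANOVA, over initial-repeat correlations of 0.8 to 0.2 and in the simulations.

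The confounding part is conditional. It matters at a gap of about two points with relief proportional to starting pain. At one point the three-level interaction test is near or below 5% in most runs, and under additive relief it stays near 5%. Every start mean, SD, correlation and anchor mix behind these rates is an assumption, because the documents give none.

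A reader might also infer that (1 + rho)/2 translates into fewer children for Primary Aim #1. It does not. The ratio assumes equal variances and a covariate unrelated to group, whereas this is an interaction between two observed factors on a bounded scale. With a true interaction of one point and equal starts, simulated power on that scale (194 versus 56) rose only from 0.24 to 0.28.

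**What to change.** - **Anchor ANOVA:** add the initial score of the same scale as a covariate, for precision.
- **Comparison by neurocognitive level:** keep the planned Fisher z test, or the fallback two-way ANOVA if it is triggered. Prespecify beside it, for each scale, a companion linear model of change on anchor, level, anchor x level, initial score and initial score x anchor. Do not enter the initial score as a main effect only. Robust standard errors are worth specifying where the cells are large enough to support them.
- **Reporting:** show initial WBF and FPS-R scores by neurocognitive group, so that a reader can see whether a material gap exists.

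The cost is SAP wording and, in the three-level fallback model, up to 3 degrees of freedom per scale (1 for the initial score, 2 for its product with the anchor), in a setting where the 'same' and 'worse' cells may be sparse. No new data are needed, and the 56 per group and the total of about 250 are unaffected.

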The frequency and nature of deviations from the pain scale script at the initial pain assessment in triage will be directly observed by the PI and audio recorded for future word-for- word analysis of deviations from the script. The audio recordings will be used to make transcripts devoid of PHI for this purpose. Field notes will be taken by the PI in order to provide context and other key observations not captured by the audio recordings. Variations from the transcript will be identified and quantified. Field notes, coupled with quantitative data of the frequency of deviations from the pain scale script and their location within the script will be analyzed by qualitative methods of interview analysis described in the Qualitative Analysis Guide of Leuven, modified to analyze our observations.⁷ Briefly, the data of the script deviations and field notes will be conceptualized, whereby the data will be filtered and the most important data clustered into concepts to prepare for analysis. The transcripts and field notes will be re-read with the concepts in mind and refined. The individual transcripts will be assessed by the constant comparative method with review of common themes and the identification of new themes. Concepts will be integrated into a conceptual framework relating to the hypothesis and discussed with the research team to obtain consensus prior to generating a final summary of concepts.

Phase 2 – Primary Aim #1:

To determine if level of neurocognitive development impacts responsivity of the WBF and FPS-R (whether the measure is able to identify changes in pain over time that are clinically important to patients) when used in the pediatric ED with children presenting with acute pain.

Hypothesis: Patients with at or above expected cognitive development will exhibit improved responsivity when using the WBF and FPS-R compared to children with lower than expected cognitive development. Those who can successfully complete behavioral tasks such as matching and grouping will exhibit improved responsivity when using the WBF and FPS-R compared to children who cannot complete such tasks successfully.

Phase 2 – Primary Aim #2:

To determine the cognitive age equivalent at which children presenting to the emergency department with acute pain can use the WBF and FPS-R accurately to self-report their level of pain at two separate time points during their ED evaluation.

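### The fallback ANOVA for Primary Aim #1 tests only the mean-change part of responsivity, and its F test has the wrong error rate if the development groups differ in both size and scatter

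*Combined protocol and SAP*

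**What the plan says.** All analysis text is in the Combined protocol and SAP, Statistical Analysis, Phase 2.

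- Measure: "Responsivity will be measured by correlating the change in the WBF and FPS-R scores before and after analgesic intervention with the anchor change" rating.
- Main test of Aim #1: "We will use Fisher's z-transformation to test if level of neurocognitive development impacts responsivity". The section explains that "The Fisher's z-transformation formally tests if the correlations between two measures (change in pain and anchor rating) differ between two groups". It asks for at least 56 children per development group.
- A second criterion, on means: "For the scales to be considered responsive, we would need to see significant reductions for the children reporting" the largest improvement, little or no reduction for those unchanged, and a rise for those worse.
- Fallback: "If the variability is limited in that most children report improvement and few report same or worsening", then "we will test for responsivity differences using a two-way ANOVA where the two factors are self reported anchor response" (three levels) and development level (two levels). "The test of interest will be the two way interaction between the anchor and the neurocognitive development level". The outcomes are the WBF change and the FPS-R change.

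For the fallback the section gives no numeric trigger, sample size, variance check or unequal-variance method. The hypothesis under Phase 2 – Primary Aim #1 is "Patients with at or above expected cognitive development will exhibit improved responsivity when using the WBF and FPS-R compared to children with lower than expected" development.

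**The concern.** The main test and the fallback have different null hypotheses. Fisher's z asks whether the change-anchor correlation is the same in both groups. A correlation falls when the mean gradient across anchor categories flattens, and also when scores scatter more widely around the same means. The interaction asks only whether the differences in mean change between better, same and worse are equal in the two groups. Scatter enters it only through the error term.

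Two consequences follow. If less developed children choose faces more erratically but with the same average, the correlation drops and the interaction stays at zero. And an ordinary two-way ANOVA pools one residual variance over all cells. If one group is both smaller and noisier, the pooled figure understates the error of the between-group comparison and the test rejects too often. If the larger group is the noisier one, the test becomes too conservative.

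A smaller below-expected group is plausible. The Exclusion criteria remove children with a history of developmental delay, and the stated minimum is 56 of about 250. What is at stake is whether a positive or negative answer to a primary aim, reached through the fallback, can be taken at face value.

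**Working it through.** **Inputs from the documents.** Total about 250 and a minimum of 56 per development group, so the most uneven split that meets the minimum is 56 and 250 − 56 = 194. The fallback is a 3 × 2 ANOVA, so the interaction has 2 numerator df and 250 − 6 = 244 residual df.

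**Assumptions, because the documents give none.** Two-sided alpha 0.05; mean change −3/0/+2 for better/same/worse in both groups; anchor shares 60/25/15%; residual SD 2 in one group and 2 to 4 in the other; pooled variance.

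**1. The plan's own figure.** The 56 belongs to the Fisher z test, and its inputs are not stated. It is consistent with n = 2[(1.960 + 0.842)/(atanh r1 − atanh r2)]² + 3. For r = 0.75 vs 0.40 the difference is 0.549, which gives n = 55.02, rounded up to 56. Other pairs with the same difference fit equally well. There is no corresponding figure for the interaction.

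**2. Scatter changes the correlation but not the interaction.** Code the anchor −1/0/+1.
- Anchor variance: 0.75 − 0.45² = 0.5475.
- Variance of the category means: 6.0 − 1.5² = 3.75.
- Covariance: 2.1 − (0.45 × 1.5) = 1.425.
- r = 1.425/√[0.5475 × (3.75 + SD²)], which is 0.69 at SD 2, 0.54 at SD 3 and 0.43 at SD 4.

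The category means are identical throughout, so the true interaction is zero. In simulation with 125 per group, SD 4 vs 2, Fisher's z rejects 88% and the interaction F about 5%. At SD 3 vs 2 the figures are 48% and 5%.

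**3. Error rate of the pooled F test.** With the same anchor shares in both groups:
- pooled variance = [(n1 − 3)SD1² + (n2 − 3)SD2²]/244
- k = (SD1²/n1 + SD2²/n2) / [pooled variance × (1/n1 + 1/n2)]
- rejection under no interaction ≈ P(F(2,244) > 3.033/k) = (1 + 3.033/(122k))^(−122)

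Example, SD 4 in the group of 56 and SD 2 in the group of 194: pooled variance = (53 × 16 + 191 × 4)/244 = 6.607. The variance the test uses is 6.607 × 0.02301 = 0.152. The true variance is 16/56 + 4/194 = 0.306. So k = 2.015 and the rejection rate is 22.4%.

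| Groups | SDs | k | Formula | Simulation |
|---|---|---|---|---|
| 56/194 | 2 / 2 | 1.00 | 5.0% | 5% |
| 56/194 | 2.5 / 2 | 1.28 | 9.6% | 10% |
| 56/194 | 3 / 2 | 1.55 | 14.3% | 15% |
| 56/194 | 4 / 2 | 2.02 | 22.4% | 22% |
| 56/194 | 2 / 4 | 0.50 | 0.3% | 0.3% |
| 125/125 | 4 / 2 | 1.00 | 5.0% | 5% |

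With a separate residual variance per group, the simulated rate in the four 56/194 rows with SD 2 in the larger group is 4.6% to 5.5%.

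**4. Sensitivity.** With means −4/0/+2 and anchor shares 70/20/10%, the pooled test at 56/194 rejects 14.5% (SD 3 vs 2) and 22.9% (4 vs 2). With shares 80/12/8% it rejects 14.5% and 22.0%. About 2% and 6% of runs respectively had a cell with fewer than two children and were dropped.

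**5. What the interaction does detect.** Halving the gradient in one group (−1.5/0/+1, SD 2 in both) gives 94% rejection at 125/125 and 79% at 56/194, against 87% and 70% for Fisher's z. If half of the below-expected children answer the anchor at random (means −4/0/+2, shares 70/20/10%), the interaction rejects 89% and 82%.

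**The case against.** The strongest reply is that the fallback is a reasonable choice. The SAP's second criterion is a pattern of mean change by anchor category, and Study Definitions describes responsivity as identifying clinically important change, not as a correlation. The interaction asks directly whether that pattern differs by development level. So a reader might infer that the fallback tests something other than responsivity, but the documents do not support that: it tests one of the two components they name. A compressed-range group with equal correlations is likewise no false alarm. By the mean criterion those children are less responsive, and the interaction is right to reject.

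The correlation is also a poor yardstick in the fallback setting. With identical means, SD 2 in both groups and 125 children each, anchor shares of 80/12/8% against 60/25/15% make Fisher's z reject 18% to 19%, and 90/6/4% against 60/25/15% about 61%. The interaction stays at 4% to 5%. Moving away from the correlation when the anchor is skewed can be defended.

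A reader might also infer that the ANOVA misses noisier reporting generally, or that its error rate is wrong as it stands. Neither holds. The blind spot is scatter that leaves every category mean unchanged, and the error rate needs unequal spread and unequal size together. The hypothesis predicts better responsivity and says nothing about residual SD; 56 is a minimum, not an expected size. The 22% figure is the far end: with entry pain of at least 4/10 the largest possible rise is 6, so an SD of 4 around a mean of +2 puts about 16% of the worse group out of range (P(Z > (6 − 2)/4) = 0.16). Also, 60/25/15% barely meets the trigger, although the more skewed shares give similar rates.

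What remains is that the plan does not say that the estimand narrows, and leaves the F test unprotected against a combination of size and spread that is plausible here.

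**Conclusion.** The point holds in limited form. In the fallback, Aim #1 is answered by the mean-gradient part of responsivity alone, while the main analysis uses a quantity that also reflects scatter. If pooled variance is used, as the unqualified term two-way ANOVA implies, the nominal 5% becomes about 10% to 22% when the below-expected group is 56 of 250 with an SD 1.25 to 2 times larger. It becomes 0.3% when the larger group has twice the SD, and stays at about 5% with equal SDs or equal groups. These figures rest on assumed means, SDs, anchor shares and group sizes. The documents do not show that the adverse combination will occur. They also do not rule it out, and the protection costs almost nothing. This should be changed, but it affects a contingency analysis and does not undermine the main test.

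**What to change.** In Statistical Analysis, Phase 2, amend the fallback as follows.

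1. Fit the same anchor-by-level model for each scale with a separate residual variance for each development level (for example generalised least squares with Satterthwaite-type df), or use a heteroscedasticity-robust test. Keep the interaction as the test of interest, at the full alpha.
2. Beside it, report each group's change-anchor correlation and its residual SD around the anchor-category means, with confidence intervals, as descriptive results.
3. State that a conclusion reached through the fallback concerns a difference in mean change pattern by anchor category, and does not by itself show equal or unequal correlation.

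Do not split alpha or make residual SD a co-primary test. The protocol never defines scatter as a criterion, and halving alpha would cut power for a halved gradient at 56/194 from 78% to 68%.

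Cost: SAP wording and a few lines of code, no new data, and slightly fewer effective degrees of freedom.
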